10.3.5.4.2 SAE Contact Information

Current SAE contact information can be found in the Study Manual.

10.3.6 *Pregnancies*

If a participant becomes pregnant during the study, she must be discontinued from study drug and monitoring of the participant and fetus should be conducted until the pregnancy outcome is known. The Investigator should notify the Medical Monitor, and a Pregnancy Notification Form should be completed. At the completion of the pregnancy, the Investigator will document the outcome of the pregnancy.

If a male participant's partner becomes pregnant during the study, the same reporting and monitoring requirements will apply, but the partner must first consent to being followed.

If the Investigator becomes aware of a pregnancy up to a month after participant's completion of the study, the pregnancy will be reported to the Sponsor's Medical Monitor and followed up as described above.

Pregnancy in and of itself is not an SAE. Complications of the pregnancy that meet seriousness criteria (e.g., hospitalization) should be reported to the Sponsor within 24 hours of knowledge by the Investigator (i.e., if the mother is hospitalized for dehydration) and an SAE form must be completed. In addition, if the pregnancy ends for any reason before the anticipated date, the Investigator should notify the Sponsor. If the outcome of the pregnancy meets the criteria for immediate classification as an SAE (i.e., postpartum complication, spontaneous abortion, stillbirth, neonatal death, or congenital anomaly), the Investigator should follow the procedures for reporting an SAE.

10.4 Appendix 4: Contraceptive and Barrier Guidance

Participants who are sexually mature and sexually active must be willing to use contraception as noted in [Section 10.4.2](#) from CCI prior to Day 1 through CCI after the last dose of study drug for females and from Day 1 through CCI after the last dose of study drug for males. If site requirements for contraception are more stringent, the site requirement will be followed.

Of note, men or women exclusively engaging in same-sex sexual activities are not required to use contraception.

10.4.1 Definitions

10.4.1.1 Non-Childbearing Potential

A woman of non-childbearing potential is defined in criterion 9 of [Section 5.1](#).

If a female participant's child-bearing potential is uncertain in the Investigator's opinion, FSH testing will be conducted at Screening (see [Table 1](#) and [Table 5](#)).

10.4.2 Highly Effective Methods of Contraception

Contraception methods that can achieve a failure rate of <1% per year when used consistently and correctly are considered highly effective. Such methods include:

- Combined (estrogen and progestogen containing) hormonal contraception associated with inhibition of ovulation:
 - Oral
 - Intravaginal
 - Transdermal
- Progestogen-only hormonal contraception associated with inhibition of ovulation:
 - Oral
 - Injectable
 - Implantable
- Intrauterine device (IUD)
- Intrauterine hormone-releasing system (IUS)
- Bilateral tubal ligation
- Vasectomized sole partner (for a participant who is a WOCBP)

For male participants only:

- Condom, with or without spermicide, or
 - At least 3 months following successful vasectomy
-

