
c) Agree to use a highly-effective method of contraception (as defined in Section 10.4) from CCI prior to Day 1 and for at least CCI following last study drug administration. Exception: Women exclusively engaging in same-sex sexual activities are not required to meet this criterion.
 
d) Must be willing to forgo ova (egg) donation for at least CCI following the last study drug administration.
 
9. Women of non-childbearing potential are defined as meeting at least 1 of the following criteria:
 
a) At least 12 months post-menopausal and has an FSH >40 mIU/mL.
 
b) Surgically sterile, defined as having a documented bilateral oophorectomy, or hysterectomy.
 
10. Male participants must be willing to follow contraceptive requirements (as defined in Section 10.4) and should not impregnate anyone while they are in the study and for at least CCI following the last dose of study drug. In addition, participant must be willing to forgo sperm donation for at least CCI following the last dose of study drug. Men exclusively engaging in same-sex sexual activities are not required to meet this criterion.
 
Exclusion criteria
 
1) Participant has a history of multiple drug allergies or of allergic reaction to an oligonucleotide or to N-acetylgalactosamine (GalNAc).
 
2) Participant has a history of intolerance or any medical condition that might interfere with SC injection(s).
 
3) History or signs or symptoms of severe (bacterial, viral, parasitic, or fungal) infection within 4 weeks prior to Screening or Day -1 Visits.
 
4) History or signs or symptoms of an acute illness (including COVID-19) within 10 days prior to dosing on Day 1 Visit. Exception: mild seasonal allergies.
 
5) Positive COVID-19 test, if applicable per site SOP, at Screening and Day -1 Visit.
 
6) Participant received a COVID-19 or any other vaccine within 14 days before dosing on Day 1 Visit or is scheduled for vaccination anytime during the study.
 
7) Participant has total bilirubin > upper limit of normal (ULN) though participants with documented Gilbert's syndrome with normal conjugated bilirubin are eligible; aspartate transaminase (AST) and/or alanine transaminase (ALT) >ULN at Screening and Day -1.
 
8) Participant has estimated glomerular filtration rate (eGFR) ≤ 60 ml/min/1.73mm² (calculated by the Cockcroft-Gault formula) at Screening and Day -1.
 
9) Participant has a positive serology for hepatitis B or hepatitis C at Screening; participants with positive hepatitis B serology may be enrolled if there is evidence the participant received HBV immunization.
 
10) Participant is known to be positive for human immunodeficiency virus (HIV) and/or positive serology for HIV 1/2 where testing is permitted per local regulations.
 
11) Participant has a history of regular alcohol consumption exceeding 14 standard drinks/week. 1 standard drink is equivalent to 14g ethanol or 5 US fluid ounces (fl oz) (150 mL) of wine (approximately 12% alcohol by volume), 12 fl oz (360 mL) of beer (approximately 5% alcohol by volume), or 1.5 fl oz (45 mL) of hard liquor (approximately 40% alcohol by volume), within 1 year prior to the Screening Visit.
 
12) Participant has a history of caffeine consumption exceeding 8 cups of coffee/day (1 cup = 8 fl oz [240mL]) within 14 days prior to first study dose, or consumption of any caffeine or chocolate containing products for 3 days prior to clinical research unit admission. Caffeine-containing food and/or beverages (e.g., tea, cola) should be considered equivalent to coffee.
 
13) Unwilling to abstain from alcohol for 48 hours prior to dosing at each of the dosing visits.
 
14) Participant has a positive alcohol test at Screening and/or Day -1 Visits.

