Study Day/ Event/ Assessment	Day -28 to Day -2	Day -1	Day 1	Day 2	Day 3	Day 15 (±3 days)	Day 29 (±3 days)	Day 30 (±3 days)	Day 31 (±3 days)	Day 8, 21, 36, 43, 50, 64, 71, 78 (±3 days)	Day 57 (±3 days)	Day 85 (±3 days)	Day 113 (±5 days)	
Informed Consent	X													
Demographics	X													
Medical History	X													
Prior/concomitant medications	X	X	X	X	X	X	X	X	X	X	X	X	X	X
Admission to CRU		X				X ^b	X ^b							
Discharge from CRU					X	X			X					

[illegible]

	Screening Period ^a	Treatment Period								Follow-up Visit				ET
Visit	1	2				4	6			3, 5, 7, 8, 9, 11, 12, 13, 14, 15, 16	10	14	15	
Study Week	Week -4 to Week 0	Week 0 CRU Stay				Week 2	Week 4 CRU Stay			Week 1, 3, 5, 6, 7, 9, 10, 11	Week 8	Week 12	Week 16	
Study Day/ Event/ Assessment	Day -28 to Day -2	Day -1	Day 1	Day 2	Day 3	Day 15 (±3 days)	Day 29 (±3 days)	Day 30 (±3 days)	Day 31 (±3 days)	Day 8, 21, 36, 43, 50, 64, 71, 78 (±3 days)	Day 57 (±3 days)	Day 85 (±3 days)	Day 113 (±5 days)	
Vital Signs ^j	X	X	X	X	X	X	X	X	X	X	X	X	X	X
Digital Continuous and Triplicate 12-lead ECG ^k	X	X		X	X	X	X				X	X	X	X
Urine Drug Screen ^l ; Cotinine; Alcohol Breath or Urine Test	X	X				X	X			X	X	X	X	X
Study Drug Administration SC Injection			X			X ^m	X							
Adverse Event Monitoring	X	X	X	X	X	X ^m	X	X	X	X	X	X	X	X

Abbreviations: AAT = alpha-1 antitrypsin; BMI = body mass index; ECG = electrocardiogram; ET = early termination; FSH = follicle stimulating hormone; PK = pharmacokinetic; SC = subcutaneous.

^a Screening assessments can occur on multiple days, provided they are within the Day -28 up to Day -2 Screening period.

^b If required per site SOP, admission on Day 14, and/or 28 is acceptable.

^c Negative serum pregnancy test at Screening for WOCBP. Negative highly sensitive urine pregnancy test documented for WOCBP on Day -1 and prior to every dose.

^d FSH only to confirm non-childbearing potential.

^e COVID-19 testing if required per site SOPs.

^f Safety laboratory tests include hematology, clinical chemistry, coagulation and urinalysis as noted in [Table 11](#). Note that for urinalysis, abnormal results on dipstick or urinalysis should lead to laboratory urinalysis testing and/or urine microscopy. Any specific safety labs indicated in [Table 6](#) will be collected according to the schedule in that table. When applicable and feasible, blood sampling should follow evaluations of vital signs and ECGs to reduce any impact on these measurements.

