5.1 Inclusion Criteria

Participants are eligible to be included in the study only if all of the following criteria apply:

1. Participant is capable of understanding and be willing to provide written informed consent prior to any study-related procedures.
 2. Participant is capable of understanding and adhering to all the requirements, procedures, instructions, and restrictions required by the protocol including scheduled visits, drug administration plan, laboratory tests, and likely to complete the study as planned.
 3. Healthy as determined by the Investigator, based on a medical evaluation, including medical history, concomitant medications, full physical examination, vital signs, laboratory tests, and ECGs at Screening and Day -1. Per Investigator's judgement, there should be no evidence of cardiovascular, pulmonary, endocrine, hepatic, biliary, gastrointestinal, neurological, hematological, immunological, metabolic, skeletal, renal, psychiatric disorders, or cancer within the past 5 years prior to Screening Visit (except localized or in situ cancer of the skin). Clinical abnormality or laboratory parameter(s) outside normal range must not be clinically significant or unlikely to introduce additional risk to the participant nor interfere with the study procedures nor the interpretation of any of the study assessments.
 4. Male or female healthy participants 18-65 years of age at Screening Visit.
 5. Participant has a body mass index (BMI) between 18 to 32 kg/m² inclusive at Screening and Day -1 Visits.
 6. Genetic testing confirming PI*MM.
 7. Participant has been a non-smoker for at least 1 year prior to screening and agrees to abstain from tobacco and nicotine containing products for the duration of the study.
 8. Women of childbearing potential (WOCBP) must be:
 - a. Non-pregnant as determined by a negative serum pregnancy test at Screening and negative highly sensitive urine pregnancy test on Day -1.
 - b. Non lactating.
-

- c. Agree to use a highly-effective method of contraception (as defined in [Section 10.4](#)) from **CCI** prior to Day 1 and for at least **CCI** following last study drug administration. Exception: Women exclusively engaging in same-sex sexual activities are not required to meet this criterion.
 - d. Must be willing to forgo ova (egg) donation for at least **CCI** following the last study drug administration.
9. Women of non-childbearing potential are defined as meeting at least 1 of the following criteria:

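### Section 10.4.2 counts a partner's vasectomy as highly effective with no interval or success condition, though it sets both for a male participant's vasectomy

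*Combined protocol and SAP*

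**What the plan says.** Section 10.4.2 opens with a general standard: "Contraception methods that can achieve a failure rate of <1% per year when used consistently and correctly are considered highly effective". It then names the accepted methods. One entry is "Vasectomized sole partner (for a participant who is a WOCBP". Its only qualifiers are that he is her sole partner and that she is a WOCBP.

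A separate sub-list follows under "For male participants only". It accepts a condom, or a vasectomy that satisfies "At least 3 months following successful vasectomy". The sub-heading confines that condition to male participants.

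The list decides eligibility. Inclusion criterion 8c in Section 5.1 requires a WOCBP to "Agree to use a highly-effective method of contraception" and refers to Section 10.4 for the definition; the synopsis repeats this. The use must start a stated time before Day 1, but that time is redacted. Section 10.4 also provides: "If site requirements for contraception are more stringent, the site requirement will be followed". No other section gives a time or success condition for a partner's vasectomy.

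**The concern.** The question is the same in both entries: is this vasectomy effective yet? The protocol asks for an interval and for success when the man is the participant, and for neither when he is the participant's partner. It gives no reason for the difference. A site that applies 8c as written can therefore accept, for a WOCBP, a vasectomy that Section 10.4.2 would reject for a male participant. Section 5 and Section 10.5.2 bar eligibility waivers, so the written criterion is what sites work from.

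At stake is whether a woman counted as protected actually is protected when she receives a drug not previously given to humans. Section 2.3 accepts that unforeseen toxicities are possible. Pregnancy also has consequences within the trial: it is a ground for unblinding (Section 6.5.1.1), requires permanent discontinuation of treatment in Period 2 (Section 7.1), and requires follow-up to outcome (Section 10.3.6).

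**Working it through.** The plan has no figure of its own to reproduce on this point. The check compares the entries and then works out which doses the missing interval could cover.

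**Comparison of the two entries in Section 10.4.2**

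| | Partner of a WOCBP | Male participant |
|---|---|---|
| Time since vasectomy | none stated | at least 3 months |
| Success of vasectomy | none stated | required |
| Criterion that relies on it | 8c | 10 |

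**Inputs for the timing**
- Dose days: Day 1 in Period 1; Days 1, 15 and 29 in Period 2 (Section 4.1.2, Tables 1 and 5). Nominal days are used and visit windows are ignored.
- 3 months = 3 × 30.44 ≈ 91 days. Calendar months give 89 to 92 days.
- L = days from the partner's vasectomy to Day 1. The documents give no values, so L is an assumption throughout.
- P = the pre-Day-1 contraception period in 8c, in days. It is redacted, so it is treated as unknown.

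**When the 3-month condition would first be met**

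Study day d falls L + d − 1 days after the vasectomy. Setting L + d − 1 = 91 gives d = 92 − L.
- L = 28: d = 92 − 28 = Day 64. With 89 days it is Day 62; with 92 days, Day 65.
- L = 60: d = 92 − 60 = Day 32. With 89 days it is Day 30; with 92 days, Day 33.
- L = 91 or more: met from Day 1.

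**Doses given before it is met**

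A dose on day k comes too early when k < 92 − L, that is, when L ≤ 91 − k. The limits are L ≤ 62 for Day 29, L ≤ 76 for Day 15 and L ≤ 90 for Day 1.

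| L (days) | Period 2 doses before 3 months | Period 1 dose before 3 months |
|---|---|---|
| up to 62 | 3 of 3 | yes |
| 63 to 76 | 2 of 3 | yes |
| 77 to 90 | 1 of 3 | yes |
| 91 or more | 0 of 3 | no |

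**How the redacted period limits this**

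A woman who relied on the vasectomy alone throughout P must have L ≥ P, so her time gap is P ≤ L ≤ 90:
- P = 28: L from 28 to 90.
- P = 60: L from 60 to 90.
- P ≥ 91: no gap.

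L below P is possible only if she used another listed method first and then changed to relying on the vasectomy. The missing success condition does not depend on P or L.

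**Pregnancy tests**

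A WOCBP is tested at Screening and on Day -1. For Period 2, footnote c of Table 5 requires: "Negative highly sensitive urine pregnancy test documented for WOCBP on Day -1 and prior to every dose". These tests detect a pregnancy; they do not prevent one. Period 1 has one dose, so every test after Day -1 follows exposure. In Period 2 a positive test stops the next dose but cannot undo earlier ones.

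**The case against.** The strongest counter-argument is that the two entries can be reconciled. Section 10.4 starts contraception for women before Day 1 but for men only on Day 1. Men have no lead-in, so their vasectomy entry needs its own interval; a woman's method must already have been in use. This could account for the timing, but only if the redacted period is about 3 months or longer. It does not account for the missing success condition, or for a woman who changes from another method to a recent vasectomy.

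The male entry is also in a separate sub-list that accepts a condom, and criterion 10 does not use the highly-effective standard that 8c uses. That is true, and the two entries are not in literal contradiction. But it leaves the women's list, under the stricter standard, with the weaker vasectomy condition.

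Third, no other WOCBP method carries an onset condition. That is also true, but vasectomy is the one method for which this section states such a condition elsewhere.

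Finally, the <1% per year standard lets a site refuse a recent or failed vasectomy, stricter site rules prevail, and pregnancy testing is frequent. These safeguards keep the gap small. None of them tells a site to apply the condition, and with up to 4 units practice could differ.

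**Conclusion.** The concern holds. Followed as written, Section 10.4.2 can count a WOCBP as using a highly effective method on the strength of a vasectomy that is too recent, or not known to have succeeded, by the protocol's own standard for men.

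Its practical size cannot be stated as a number of women: the documents do not give the number of WOCBP or how many would rely on a partner's vasectomy. The day counts above are illustrations that rest on assumed values of L and on 3 months being about 91 days. The time gap for a woman relying on vasectomy alone is empty if P is 91 days or more; the success gap stays whatever P is. This is a small participant-protection point, worth correcting because it is cheap. It affects no endpoint, analysis or sample size.

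**What to change.** In Section 10.4.2, extend the vasectomized-partner entry with the condition already used for male participants, "At least 3 months following successful vasectomy", and keep the sole-partner and WOCBP qualifiers. Because 8c and the synopsis refer to Section 10.4, no other text needs to change.

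The cost is one list entry, with no new visit, procedure or data item. The protocol does not say how success is established for male participants, and the added words would carry the same silence. If the sponsor wants documentary proof for a partner, who is not a participant, that would be an extra step beyond this fix.

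A woman whose partner's vasectomy is under 3 months old would need another listed method until the interval has passed. If she used none during the pre-Day-1 period, her dosing would wait until 8c is met.

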10.5 Appendix 5: Management of Protocol Amendments and Deviations

10.5.1 Modification of the Protocol

Changes in this research activity, except those necessary to remove an apparent, immediate hazard to the participant, must be reviewed and approved by the Sponsor or designee.

Amendments to the protocol must be submitted in writing to the Investigator's IRB/EC and regulatory authorities for approval before participants can be enrolled into an amended protocol.

10.5.2 Protocol Deviations

A deviation from the protocol is any change, divergence, or departure from the study design or procedures defined in the protocol and associated manuals, ICF, recruitment process, or study materials approved by the Sponsor, Investigator, and the IRB/EC.

Important protocol deviations are a subset of protocol deviations that might significantly affect the completeness, accuracy, and/or reliability of the study data or that might significantly affect a participant's rights, safety, or well-being. For example, important protocol deviations might include enrolling participants in violation of key eligibility criteria designed to ensure a specific study population or failing to collect data necessary to interpret primary endpoints, as this may compromise the scientific value of the study.

All processes and procedures defined in this protocol must be adhered to. Emergency departures from the protocol that eliminate an apparent immediate hazard to a particular participant and that are deemed by the Investigator as crucial for the safety and well-being of that participant may be instituted for that participant only and documented as deviations. The Investigator will contact the Medical Monitor as soon as possible regarding such a deviation. These departures do not require preapproval by the IRB/EC; however, the IRB/EC and Medical Monitor must be notified in writing as soon as possible in accordance with the IRB/EC policies after the departure has been made.

Protocol deviations will be documented by the clinical monitor in the clinical study management system and on monitoring reports throughout the course of monitoring visits. Investigators will be notified in writing by the monitor of deviations. As required by local regulatory authorities, the Investigator will notify the IRB/EC of any applicable protocol deviations in a timely manner.

No protocol deviations to eligibility, also known as waivers, will be permitted.

10.6 Appendix 6: Grading of Injection Site Reactions

Individual signs or symptoms (e.g., erythema, swelling, etc.) at the injection site reported by a participant following study drug administration will be recorded as an injection site reaction and as an AE if grade 1 or more.

Grading of Injection Site Reactions (FDA, 2007)

Local Reaction to Injectable Product	Mild (Grade 1)	Moderate (Grade 2)	Severe (Grade 3)	Potentially Life Threatening (Grade 4)
Pain	Does not interfere with activity	Repeated use of non-narcotic pain reliever >24 hours or interferes with activity	Any use of narcotic pain reliever or prevents daily activity	Emergency room (ER) visit or hospitalization
Tenderness	Mild discomfort to touch	Discomfort with movement	Significant discomfort at rest	ER visit or hospitalization
Erythema/Redness	2.5 – 5 cm	5.1 – 10 cm	>10 cm	Necrosis or exfoliative dermatitis
Induration/Swelling*	2.5 – 5 cm and does not interfere with activity	5.1 – 10 cm or interferes with activity	>10 cm or prevents daily activity	Necrosis

* Induration/Swelling should be evaluated and graded using the functional scale, as well as the actual measurement.

